2. INTRODUCTION

2.1. Background and Rationale

Tuberculosis (TB) caused by the bacterium *Mycobacterium tuberculosis* (*M.tb*), remains the deadliest infectious disease globally. According to the World Health Organization (WHO) global TB report, the burden of multidrug-resistant TB (MDR-TB); i.e., resistance to at least rifampicin and isoniazid, has increased by an annual rate of over 20% during the period 2009-2017(1). In 2019, the global burden of Rifampicin-Resistant TB (RR-TB) was estimated at 465,000 cases, 78% of which was MDR-TB. Sub-Saharan Africa carries 25% of the global burden of drug-resistant TB (DR-TB) (2). Successful management of DR-TB is hampered by difficulties in both diagnosis and treatment, fuelling the ongoing transmission of DR-TB (3). In order to achieve the targets of the WHO End TB strategy by 2035, a 90% decrease in TB incidence and a 90% reduction in TB mortality is required between 2015-2035. In line with this ambitious target, there is an urgent need for new diagnostic and therapeutic approaches in order to improve the diagnostic accuracy and timely initiation of treatment for DR-TB (4).

Globally, health systems have failed to effectively implement DR-TB testing and treatment regimens, evidenced by dismal treatment success rates. In 2019, WHO reported treatment success rates of approximately 57% for DR-TB (2). Historically, the treatment of DR-TB has been challenging due to prolonged duration of treatment (20-24 months), severe toxicities and sub-optimal treatment success. Given the complex nature and duration of DR-TB treatment, significant medication adherence issues arise thereby contributing to poor treatment completion rates. Until recently, the WHO guidelines for MDR-TB (including RR-TB) and extensively drug-resistant TB (XDR-TB) incorporated the use of injectable aminoglycosides and a fluoroquinolone as the backbone of treatment (5). These agents were considered significant contributors in obtaining a successful treatment outcome. However, the use of these drugs has been associated with severe discomfort and side-effects including hearing loss and renal impairment, which, in addition to personal suffering, affect treatment adherence and completion (6). Given the toxicity associated with the second-line injectable drugs, WHO recently modified DR-TB treatment guidelines no longer recommend the use of second-line injectables as part of the MDR-TB regimen. In the latest guidelines, WHO re-classified anti-TB drugs into three main groups according to the available evidence on DR-TB drug effectiveness and safety. These include; Group A (bedaquiline, linezolid, moxifloxacin or levofloxacin), Group B (clofazimine, and cycloserine or terizidone) and Group C (ethambutol, delamanid, pyrazinamide, imipenem-cilastatin, meropenem, amikacin/streptomycin, ethionamide/prothionamide, p-aminosalicylic acid). In line with this recommendation the definition of XDR-TB on the basis of resistance to second-line injectables became less clinically relevant. Thus, leading to 2021 revised definitions for DR-TB. According to the update, pre-XDR is defined as RR-TB or MDR-TB with additional resistance to a fluoroquinolone. XDR-TB is now defined as RR-TB or MDR-TB with resistance to a fluoroquinolone and at least one other group A drug. The definition for MDR-TB remains the same.

The diagnosis of DR-TB poses a further obstacle to attaining successful treatment. In high-burden DR-TB countries, the diagnosis of MDR-TB in most settings is a proxy diagnosis made

through a multi-step testing cascade. Currently, the front-line molecular diagnostic assay for drug resistance is Cepheid Xpert MTB/RIF or Xpert MTB/Ultra, which detects the presence of *M.tb* bacilli and simultaneously detects RR-TB. Whilst rapidly identifying patients eligible for MDR-TB treatment, the test is limited to the detection of RR only (7, 8). Patients who display RIF resistance receive reflex testing which includes resistance to fluoroquinolones and second-line injectables using standard phenotypic drug susceptibility testing (pDST) and the Hain Line Probe Assays (LPA 1 and 2), which detect resistance to isoniazid, rifampicin, fluoroquinolones and second-line injectable agents (9). Drug susceptibility testing (DST) for all other drugs is conducted using phenotypic testing methods. However, following a rapid diagnosis by Xpert MTB/RIF or Xpert MTB/Ultra, all follow-on testing is conducted at a regional laboratory thereby increasing the turn-around times for providing a comprehensive resistance profile. Furthermore, these DST methods have several limitations. Although LPA testing can be rapidly performed on sputum samples, LPAs require specialised laboratory facilities, longer turnaround time and are associated with a high indeterminate rate (~30%) in smear-negative patients (10). Phenotypic DST (pDST) techniques require approximately 4-6 weeks and result interpretation are compounded by issues with the established critical drug concentrations used to predict resistance and poor performance for certain drugs such as ethionamide and pyrazinamide. Currently, DR-TB patients are initiated on empiric treatment, which is modified as DST results become available, resulting in a 4-6-week delay in initiation of appropriate treatment. As a result of this sub-optimal testing cascade, many patients may receive a limited number of effective drugs in the regimen, increasing the risk of amplifying drug resistance and ongoing transmission of DR-TB (3). A further challenge which hinders the diagnosis and treatment of DR-TB is the lack of susceptibility testing for isoniazid resistance by assays available at the point where the patient enters the care cascade, i.e. Xpert MTB/RIF, Xpert MTB/RIF Ultra, or the Truenat assays. As a consequence, isoniazid mono-resistant TB patients (HR-TB; i.e. patients who display INH resistance in the absence of RIF resistance) are not appropriately diagnosed. This sub-set of patients receive standard DS-TB treatment, thereby increasing the risk of amplifying drug resistance (11).

In the last few years, the DR-TB treatment landscape has been transformed drastically by several landmark changes to DR-TB guidelines. These include: reports confirming safety and the survival benefit of Bedaquiline (BDQ) for MDR-TB (12); WHO endorsement of the standard 9 month short-course regimen for MDR-TB and the Short Standardized Regimen For The Treatment Of Rifampicin-Resistant Tuberculosis (STREAM ; NCT02409290) study results demonstrating non-inferiority of shorter DR-TB regimens to longer regimens (13, 14); the replacement of second-line injectables with BDQ in the standard short-course DR-TB regimen, resulting in the first all-oral regimen for DR-TB (15); and the results of the novel 6 month BPaL (BDQ, pretomanid, and linezolid) regimen for XDR-TB. These changes have resulted in a rapid transition to all-oral treatment options for DR-TB. Thus, the current study aims to implement diagnostics with proven clinical efficacy to guide treatment with novel, all-oral regimens as efficacy data from clinical studies emerge. Furthermore, the lack of specific outcome data for the novel diagnostic assays represents a significant implementation research gap which the study will address. Given the state of access to DR-TB diagnosis and treatment globally, the implementation of shorter, efficacious, and more importantly, less toxic regimens than the conventional long regimen holds significant promise in improving dire treatment success rates. Notably, this approach could potentially preserve the potency of the new drugs included in the shorter regimens by preventing the rapid amplification of resistance.

2.2. Epidemiology of DR-TB

South Africa, Ethiopia and Nigeria feature prominently among the 30 high-burden TB countries with significantly overlapping epidemics of TB, Human Immunodeficiency Virus (HIV) and MDR-TB. The 30 high-burden countries collectively contribute to approximately 90% of the global disease burden. South Africa, in particular, remains among the few countries with a TB incidence exceeding 500 cases per 100,000 population with approximately 360,000 cases of TB reported during 2019. In 2019, 13,005 and 406 cases of laboratory confirmed RR/MDR-TB and XDR-TB were reported in South Africa, respectively. The overall treatment success rate was 71% for drug-susceptible TB (DS-TB), 60 % for RR-TB/ MDR-TB and XDR-TB. Ethiopia has a TB incidence rate of 140 cases per 100,000 population with approximately 157,000 cases of TB reported during 2019. In 2019, 658 and 4 cases of laboratory confirmed RR/MDR-TB and XDR-TB were reported in Ethiopia, respectively. The overall treatment success rate was 88% for DS-TB, and 75% for RR-TB/ MDR-TB and XDR-TB. Nigeria records a TB incidence rate of 219 cases per 100,000 population with approximately 440,000 cases of TB reported during 2019. In 2019, 2,384 and 16 cases of laboratory confirmed RR/MDR-TB and XDR-TB were reported in Nigeria, respectively. The overall treatment success rate was 87% for DS-TB, 77% for RR-TB/ MDR-TB, and no data were available for the XDR-TB patients (2).

2.3. Evidence for novel regimens and diagnostics proposed in this study

2.3.1. Novel, all-oral treatment regimens for DR-TB

Historically, MDR-TB and XDR-TB patients have been treated with a multi-drug treatment regimen which comprises of an intensive phase of treatment of 8 months and a total duration of treatment of 20-24 months. For patients with RR-TB or MDR-TB who were not previously treated with second-line drugs and for whom resistance to fluoroquinolones and second-line injectable agents was excluded or is considered highly unlikely, a shorter treatment regimen (STR) still including an injectable, was recommended. This STR was evaluated in Stage 1 of the STREAM trial and is composed of high-dose later generation fluoroquinolone, clofazimine, pyrazinamide and ethambutol throughout, supplemented by amikacin, prothionamide, and high-dose isoniazid in the intensive phase. The treatment duration of the intensive phase is four months (extended to a maximum of six months until sputum smear conversion), and the duration of the continuation phase is five months. In December 2019, WHO issued a rapid communication encouraging countries to replace the injectable in this regimen with BDQ and use the all oral bedaquiline based STR as the preferred option.

In addition to this newly recommended shorter all-oral MDR-TB regimen, there are other shorter regimens currently being evaluated in clinical trials for the same and different patient groups. Many of these regimens employ new or repurposed medicines, which have been shown to be effective in clinical trials. These regimens have common desirable features: good tolerability, all-oral and with shorter treatment duration.

One such regimen is the BPaL regimen which consists of BDQ, pretomanid and linezolid given for 6 months. Currently, the BPaL regimen is the most appropriate alternative for the treatment of pre-XDR TB (MDR with additional fluoroquinolone resistance) and XDR-TB (pre-XDR with resistance to at least one additional Group A drug). The efficacy of the regimen was evaluated

in a single-arm randomized controlled trial which demonstrated that 90% of patients recorded a favourable treatment outcome. Treatment associated toxicity linked to the use of linezolid within the regimen was reported as manageable with dose reduction and interruption of linezolid use (16). The BPaL regimen recently received Food And Drug Administration (FDA) approval for use in people with DR-TB or treatment-intolerant/non-responsive MDR-TB or patients for whom there is no other viable as per WHO recommendations (17).

Another novel, short-course regimen under evaluation is the BPaMZ regimen indicated for use in HR-TB, RR-TB and MDR-TB is currently in late-stage clinical development. The regimen incorporates the use of two novel drugs, BDQ and pretomanid, in combination with pyrazinamide and moxifloxacin (SimpliciTB study). Pre-clinical data in a murine model demonstrated potent sterilising activity (18). Phase 2B human study data indicates superior efficacy of the novel combination in patients with DS-TB and MDR-TB (19). A phase 3 trial of the BPaMZ regimen (SimpliciTB; NCT03338621) is currently evaluating the potential to both shorten treatment to 4 months for patients with DS-TB and also effectively treat patients with RR- or MDR-TB (as a 6-month regimen, because of the higher risk of associated resistance to pyrazinamide) (20). Modelling analysis on the projected patient outcomes using the BPaMZ regimens indicates that universal implementation of the regimen has the potential to increase the percentage of patients with RR-TB who are cured from 60% to nearly 90% and maintain nearly 90% cure among patients with DS-TB. Further, the regimen could reduce treatment duration by two months and reduce infectious person-time by 50% (RR-TB) (21).

The current programmatic DR-TB treatment regimens for each country and the proposed novel interventions are described in Table 2. Novel DR-TB regimens under evaluation will be considered for inclusion by the TRiAD Joint Steering Committee (JSC) once sufficient safety and efficacy data becomes available.

2.3.2. The Xpert MTB/XDR Assay

The GeneXpert instrument platform is an automated cartridge-based system for TB diagnosis. The WHO endorsed the use of the Xpert MTB/RIF assay for the GeneXpert platform in 2010 and the assay has since been widely used in TB programs. The Xpert MTB/RIF assay was subsequently replaced by the Xpert Ultra assay which demonstrated improved sensitivity in paucibacillary disease. However, for RR-TB patients, the Xpert MTB/RIF and Ultra assays provide no further information on the resistance profile of the infecting strain type.

The Xpert MTB/XDR cartridge, a new diagnostic that is being evaluated in this study, intended for use as a reflex test. The assay includes eight genes and promoter regions in *M. tb* allowing for the detection of resistance to isoniazid, aminoglycosides and fluoroquinolones, ethionamide and the second-line injectables, enabling the diagnosis of pre-XDR TB in combination with Xpert MTB/RIF or Ultra. This assay showed excellent analytical performance in a clinical study performed at two sites with 100 sputum and 214 clinical isolates. The assay demonstrated a sensitivity of 94-100% and a specificity of 100% for all drugs except for ethionamide in comparison to sequencing. The sensitivity and specificity when compared to phenotypic drug-susceptibility testing (DST) were in the same range (22, 23).

The Xpert MTB/XDR assay is undergoing external assessment in the Xpert MTB/XDR clinical evaluation trial (NCT03728275), wherein the diagnostic accuracy of the assay and its use in diverse clinical settings is being evaluated amongst 600 patients in multicentre clinical evaluation (20). The MTB/XDR assay incorporates the same single-step specimen processing as the Xpert MTB/RIF and Ultra and can be implemented with minimal staff training and biosafety requirements. Existing GeneXpert instruments have the potential to be upgraded contemporaneously by upgrading software and performing a 10-colour calibration. These are significant features that would permit Xpert MTB/XDR to be used in peripheral sectors of the global health care system, where more rapid identification of expanded drug resistance may improve therapeutic decision-making. WHO has endorsed the use of Xpert XDR for diagnosis of TB drug resistance as of June 2021 (<https://www.who.int/publications/i/item/9789240029415>).

The focus of this protocol is to utilise the Xpert MTB/XDR assay to triage participants by promptly identify varying resistance profiles in order to guide the selection of appropriate treatment regimens. With optimal implementation, this new test should improve the selection of appropriate regimens, reducing time to appropriate treatment and improving patient outcomes (22, 24). Given the recent updated definition, the Xpert XDR assay will diagnose pre-XDR-TB. Additional DST to BDQ and linezolid (LZD) is required to define XDR-TB.

2.3.3. Tuberculosis-Molecular Bacterial Load Assay (TB-MBLA)

The TB-MBLA is a novel, quantitative Reverse Transcription PCR (RT-qPCR) that uses 16S-ribosomal RNA (rRNA) targets to quantify the *M.tb* bacillary load over the course of treatment in real-time (25). A major limitation of the current TB diagnostic and management algorithm is the lack of a sensitive and rapid assay for evaluation of treatment efficacy and predicting treatment response. Current therapeutic monitoring is dependent on *M.tb* bacterial load monitoring from clinical samples inferred from Mycobacteria Growth Indicator Tube (MGIT) time to a positive result (TTP) and smear microscopy. This poses a challenge as most settings where patients first enter the care cascade have limited availability of culture resources due to the cost of specialised laboratory infrastructure and training requirements. When resources are available, culture-based results are not always made available in a clinically relevant timeline to inform timely clinical decision making. This is compounded by factors such as specimen transport, type of media, and decontamination to eliminate non-mycobacterial flora which compromise the consistency of culture.

In addition, culture time-to-result is long and depends on the patient TB bacillary burden. This means that patients with a lower bacillary burden wait longer for results than patients presenting with a higher bacillary burden. Further, sputum culture conversion is only weakly predictive of long-term patient outcome for regimens but not individuals, limiting its utility to individual and clinical trial management. Smear microscopy, an approved routine treatment monitoring method, is less sensitive and cannot distinguish viable and dead bacilli. The TB-MBLA uses abundant 16S-rRNA as a target and can accurately quantify *M.tb* viable bacillary load directly from patients' sputum over many weeks of treatment and has the potential to replace culture, offering a promising solution and improved precision in clinical care. The assay rapidly measures patient tuberculosis bacillary burden and its change in response to anti-TB therapy, enabling the clinician to make an informed decision on patient progress. This

ability avoids challenges related to culture (e.g. time to results and contamination) and gives TB-MBLA the potential to eventually replace microscopy and culture for treatment response monitoring (26-28).

To date, the assay has been evaluated in three high TB burden, low-resource settings in Africa through the European and Developing Countries Clinical Trials Partnership (EDCTP) funding. The data showed that TB-MBLA reduces time to detection of *M. tb* bacillary loads from weeks to hours, reproducible in different laboratory settings and has the potential to inform real time clinical decision of patient treatment and expedite TB drug trials (29). Furthermore, bacillary load measured by TB-MBLA concurs with bacillary load measured by standard MGIT culture (30) and can accurately distinguish the bactericidal effect of different anti-TB regimens (31). The current study provides a unique opportunity to evaluate the role of TB-MBLA in monitoring treatment response in participants receiving varying DR-TB regimen.

2.4. Potential Benefits

There will be a direct benefit to patients who participate in this study. Participants will have access to novel drugs, diagnostics and improved treatment monitoring, not otherwise available through standard of care practice. We believe that the diagnostic methods and drugs used in this study could significantly improve TB treatment outcomes. Additionally, a rapid diagnosis coupled with initiation of appropriate treatment could potentially reduce the number of participants that are lost in the care cascade during this period. Generating evidence through implementation research on the feasibility, acceptability and cost effectiveness of novel diagnostics in improving DR-TB outcomes will fast-track translation of these study findings into policy and practice for maximum public health benefit. Given the development of the novel tests and the importance of the public health approach in triaging DR-TB participants to suitable all-oral regimens, a study evaluating the strategy is warranted. Finally, given the delays in DR-TB diagnosis, and appropriate treatment initiation, high toxicity of drugs in use, identifying strategies to improve DR-TB outcomes are important to the success of TB programmes globally.

2.5. Potential Harm

Diagnostics

The risk benefit ratio will vary by each type of resistance pattern detected. Detection of resistance conferring mutations to multiple drug classes would be beneficial to those infected with these strain types compared to those without any detectable resistance. Use of the Xpert MTB/XDR diagnostic and translation of test results for treatment modification does not preclude access to all other available diagnostic tests for DR-TB in the study settings. Until this study is completed, there is no way of knowing for sure whether a novel diagnostic that guides use of short-course DR-TB treatment will improve treatment outcomes in DR-TB participants. For this reason, there is a risk that one could be receiving DR-TB drugs that may not be beneficial.

Therapeutics

Risk of treatment related toxicity with DR-TB medication is the same for all participants exposed to given DR-TB regimen. These risks include drug toxicities from DR-TB medication

and drug interactions (e.g., between DR-TB treatment and Antiretroviral Treatment). While this study will be using several new drugs in novel regimens, stringent safety assessments from human trials conducted using these regimens have been documented and will be closely monitored. Several strategies have been implemented within this study to ensure safety of all participants should we identify any safety concerns. These include; clinical observation and referral for clinical care should participants experience untoward adverse events, safety monitoring and reporting in real time to the study safety monitoring committee and external review of all safety reports by local ethics committees and independent Data Safety Monitoring Board (DSMB).

3. DEFINITIONS OF DR-TB

- HR-TB is defined as resistance to at least isoniazid without rifampicin resistance
- RR-TB is defined as resistance to at least rifampicin without isoniazid resistance

Definitions of MDR-TB, pre-XDR and XDR-TB in background sections of this protocol refer to old WHO definitions:

- MDR-TB; resistance to at least rifampicin and isoniazid
- Pre XDR-TB; strains that fulfil the definition of MDR-TB with additional resistance to the aminoglycosides or fluoroquinolones
- XDR-TB; strains that fulfil the definition of MDR-TB with additional resistance to the aminoglycosides and fluoroquinolones.

For the purpose of defining DR-TB categories in the current study we will utilise updated 2021 WHO definitions to categorise pre-XDR-TB and XDR-TB (32)

- Pre-XDR TB; strains that fulfil the definition of RR-TB/MDR-TB with additional resistance to any fluoroquinolone
- XDR-TB; strains that fulfil the definition of RR-TB/MDR-TB with additional resistance to any fluoroquinolone and at least one additional group A drug (BDQ or LZD).

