Study Duration	48 months: study enrolment will occur over 12 -18 months
Sample Size	A total of 1280 participants will be enrolled between 2 prospective study cohorts: Cohort 1 (newly diagnosed DR; rifampicin resistance [RR-TB] participants; n=880) and Cohort 2 (rifampicin sensitive and isoniazid, fluroquinolone and or second line injectable drug (SLID) resistant participants; HR-TB; n=400). Data from a historical cohort (Cohort 3; n=220) of RR-TB participants that accessed DR-TB care at each implementing site over the last 2 years (approximately 24 months) prior to study start.

Study sites	South Africa (n=2), Nigeria (n=6) and Ethiopia (n=5)
Study population	Adult participants (18 years and over) who test positive for pulmonary M.tb with HR-TB or RR-TB will be approached for study participation
Study intervention	Xpert MTB/XDR assay as a triage test to guide early initiation of an appropriate all-oral DR-TB treatment regimen

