6.2. Selection of Participants

Approximately 4800 participants will be screened across the 13 sites (in South Africa, Nigeria and Ethiopia) to enrol 1280 eligible participants. All presumptive TB patients presenting for diagnosis at the study sites will be approached for screening. Each of the sites will also contribute to the historical cohort as described below.

6.2.1. Selection of cohort 1

880 RR-TB (n=440 in SA, n=220 in Nigeria and n=220 in Ethiopia) participants will be enrolled into Cohort 1. Each participant in cohort 1 will be followed up for the duration of TB treatment and passively thereafter to a maximum of 18 months from TB treatment initiation.

6.2.2. Selection of cohort 2

400 HR participants into Cohort 2 (n=200 in SA, n=100 in Nigeria and Ethiopia). Each participant in cohort 2 will be followed up passively for the duration of TB treatment and passively thereafter to a maximum of six months.

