6.2.3. Selection of Historical Cohorts

Each CRS will build a dataset of historical RR-TB participants that were diagnosed and started on treatment within 12 - 18 months prior to starting enrolment of the study at each of the clinical research sites. Clinical and laboratory data from this retrospective cohort will be obtained from treatment registers, participant charts and laboratory databases at each of the clinical research sites. The following data variables will be extracted: date of birth, or age, sex, HIV and ART status, facility or clinic, year and month of treatment, type of DR-TB, certainty of diagnosis (confirmed by DST or presumed, i.e., contact of DR-TB source case or failing adherent first-line TB treatment), disease classification, treatment start date and any bacteriological results on treatment (date, mycobacterial culture, DST and genotypic results), where relevant. Data on all drugs from previous DR-TB treatment regimen, DR-TB Outcomes: cure, completion, default, death, loss to follow up (LTFU) will be abstracted. Historical data will be collected on specially designed case report forms (CRF) and will be subject to routine quality assurance/control QA/QC of data to ensure maximum quality. Bias by time period and by other confounders such as HIV, gender and age, will be controlled for in the analysis. No historical data will be generated for cohort 2, as no routine data on HR-TB is available.

6.3. Participant Inclusion Criteria for cohorts 1 and 2

1. Ambulant adults \geq 18 years of age
2. Newly diagnosed PTB patients receiving less than 5 days of treatment since new diagnosis:
 - a) Cohort 1: < 5 days of DR-TB treatment
 - b) Cohort 2: < 5 days of INH mono-resistant TB treatment preceding study entry for the current TB episode, or
3. Sputum positive (smear and or culture) TB patients classified as failing first line treatment
4. Any currently available Nucleic Acid Amplification Tests for drug-resistance detection changes/assay positive for M.tb infection with:
Cohort 1: at least Rifampicin resistance

- Cohort 2: Rifampicin susceptible co-occurring with INH, fluoroquinolone, ethionamide or aminoglycoside resistance (detected by Xpert XDR) occurring alone or in combination
5. Capacity to provide informed consent
 6. HIV infected and uninfected participants are allowed in the study. Participants already on ART will be allowed in the study provided the ART regimen in use has no contraindications to the proposed TB drug regimen

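### Section 3 defines RR-TB so that it excludes MDR-TB, and the historical comparator is selected by that label with no resistance criterion of its own

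*Protocol*

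**What the plan says.** Section 3 gives the study's working definitions. It says that "RR-TB is defined as resistance to at least rifampicin without isoniazid resistance", and lists separately "MDR-TB; resistance to at least rifampicin and isoniazid". Read together, the two classes do not overlap. Section 3 says that its older definitions of MDR-TB, pre-XDR-TB and XDR-TB belong to the background sections. It places no such limit on the RR-TB line.

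Other parts of the Protocol use RR-TB inclusively. Section 2.1 says of the global RR-TB burden that it "was estimated at 465,000 cases, 78% of which was MDR-TB". Section 6.6 sends participants with RR-TB into cohort 1 and screens them for further resistance.

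For cohort 1, section 6.2.1 says "880 RR-TB (n=440 in SA, n=220 in Nigeria and n=220 in Ethiopia) participants will be enrolled into Cohort 1", and section 6.3, criterion 4, supplies the operative rule: "Cohort 1: at least Rifampicin resistance".

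For the comparator, section 6.2.3 says "Each CRS will build a dataset of historical RR-TB participants". It adds a time window, a list of variables and some named confounders, but no resistance criterion. Table 1 also calls these patients RR-TB. Footnote 5 to the study schema instead calls the historical dataset DR-TB patients.

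Under section 9.2, both primary endpoints (time to resistance-appropriate treatment and favourable outcome) compare cohort 1 with this historical cohort.

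**The concern.** Who belongs in the comparator is a matter of eligibility, and the Protocol has to settle it. Cohort 1 does not depend on the section 3 definition, because criterion 4 says what is needed. The historical cohort does depend on it, because the label is the only selection rule given. Each site builds its own dataset, so the ambiguity would be resolved site by site, and the primary comparisons are stratified by site.

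An abstractor who looks up RR-TB in section 3 would set aside every record with isoniazid resistance. At that site the historical group would contain no MDR-TB while cohort 1 contained it. Time to a regimen that fits the resistance pattern depends on the pattern by construction, and treatment outcome may depend on it too. A before-and-after difference would then mix the effect of the intervention with a difference in case mix.

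**Working it through.** **1. The plan's own figures.** Section 9.1 takes 74% against 85% favourable outcome, n = 220 and 80% power. No alpha is stated, so I assume two-sided 0.05.

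Power = Φ[(|p2 − p1| − 1.96·SE0) / SE1]. With 220 per arm, SE0 = √(2 × 0.795 × 0.205 / 220) = 0.0385 and SE1 = √((0.74 × 0.26 + 0.85 × 0.15) / 220) = 0.0381. Power = Φ[(0.11 − 0.0754) / 0.0381] = 0.818. With 15% loss in the prospective arm only (220 against 187) power is 0.782; with loss in both arms (187 each) it is 0.752. The stated 80% is reproduced under the first two variants. None of them uses the definition of RR-TB, so correcting the definition leaves n unchanged.

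**2. The uses of the term, side by side.**

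| Place | Meaning of RR-TB, or group described |
|---|---|
| Section 3 | Rifampicin resistance, isoniazid resistance excluded |
| Section 2.1 | Inclusive: 78% of RR-TB is MDR-TB |
| Sections 6.2.1 and 6.6 | Label for cohort 1, before further resistance is known |
| Section 6.3, criterion 4 | Cohort 1 rule: any rifampicin resistance |
| Table 1, section 6.2.3 | Label for the historical cohort, no further rule |
| Schema footnote 5 | Historical cohort described as DR-TB |
| Section 9.1 | Comparator success taken from MDR-TB (63%, range 57% to 74%); an XDR prevalence among MDR cases applied to all 880 (880 × 4.3% = 37.8, given as 38) |

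Section 3 is the odd one out. The last row matters most for intent: the planned comparator rate is an MDR-TB rate, so the planners expected MDR-TB patients in the comparator.

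**3. Head count under the literal reading.** Assume that the global 78% in section 2.1 applies at the sites. Then 0.78 × 880 = 686 of cohort 1 would be MDR-TB and 880 − 686 = 194 would not. A historical group selected strictly by section 3 would have no MDR-TB. Only the 194 would have historical counterparts of the same isoniazid status. For the 686, the before-and-after effect could be had only by extrapolation.

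**4. Illustration of what could follow.** Let d be the success proportion in MDR-TB minus that in isoniazid-susceptible RR-TB. The documents do not give d, so the values below are assumptions. Let f be the share of historical records selected under the literal reading. Expected success is s + 0.78·d in cohort 1 and s + 0.78·(1 − f)·d in the historical group, so the case-mix bias is 0.78·f·d.

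With f = 1, 220 per arm, 74% in the historical group and a true gain of 11 points:

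| d (points) | Bias (points) | Power |
|---|---|---|
| −10 | −7.8 | 0.12 |
| −5 | −3.9 | 0.43 |
| 0 | 0 | 0.82 |
| +5 | +3.9 | 0.98 |
| +10 | +7.8 | above 0.99 |

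With no true gain, d = +5 gives a significant result with probability 0.16, and d = +10 with probability 0.51. If only half the records were selected literally (f = 0.5), d = −5 gives 0.78 × 0.5 × (−5) = −1.95 points. These figures show sensitivity and are not an estimate.

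**The case against.** The best defence is that nobody would read the Protocol this way. Cohort 1 carries the same RR-TB label, so the natural reading of the label in section 6.2.3 is the one that holds for cohort 1. Section 6.2.3 extracts the type of DR-TB, which would serve little purpose if MDR-TB were excluded. It also provides for presumed cases without susceptibility testing, who could not be shown to be isoniazid-susceptible. The schema footnote speaks of DR-TB, and section 9.1 plans on an MDR-TB success rate. All this stands, and it makes inclusive intent likely. It does not remove the problem, because the section written to settle the meaning says the opposite, and the comparator has no rule that overrides it.

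A second defence is that resistance type is collected, multivariable adjustment is planned for both primary endpoints, and the confounder list is open-ended, so the full covariate set may be in a statistical analysis plan. That is fair for ordinary imbalance. It does not help where one group has no MDR-TB at all.

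Four stronger readings might be inferred and are not supported:

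- *The Protocol selects the two groups differently.* It states no such difference. The divergence is a risk created by the wording.
- *The definition contradicts itself.* It is coherent: rifampicin resistance, possibly with other resistance, but not to isoniazid. It parallels the HR-TB line above it.
- *A literal comparator would be rifampicin mono-resistant TB only.* Section 3 lets RR-TB carry fluoroquinolone resistance, since pre-XDR-TB is built on RR-TB or MDR-TB.
- *The analysis by type of DR-TB in section 9.2 uses two meanings of RR-TB.* For that breakdown, section 3 gives separate RR-TB and MDR-TB classes.

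**Conclusion.** The definition in section 3 is wrong for the way the Protocol uses the term, and it bears on who enters the comparator for both primary endpoints. This is a risk from ambiguous wording, not a stated difference in selection, and the intended meaning is probably inclusive.

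Neither the size nor the direction of any bias can be derived from the documents. They give no outcome difference by isoniazid status, and Table 2 puts RR-TB and MDR-TB in the same short-course class, so no difference should be presumed. The figure of 686 of 880 rests on a global share carried over to these sites. The bias figures rest further on assumed values of d and on literal selection. What does not rest on assumption is the lack of overlap: wherever section 3 is followed to the letter, MDR-TB patients in cohort 1 have no historical counterpart.

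**What to change.** Four wording changes:

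1. In section 3, define RR-TB as any rifampicin resistance, with or without resistance to isoniazid or other drugs.
2. Call the narrow class rifampicin-resistant, isoniazid-susceptible TB, so that the analysis by type still has separate categories. The term mono-resistant does not fit, because the class can include fluoroquinolone resistance.
3. In section 6.2.3, state for the historical cohort the same resistance criterion as criterion 4 of section 6.3.
4. Align the descriptions of the historical cohort in Table 1 and in footnote 5 to the schema.

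The cost is a definitional amendment; sample size, procedures and endpoints are unchanged. It should be made before historical abstraction starts. If abstraction has begun, each site should confirm which meaning it used, and any records left out for isoniazid resistance would have to be abstracted.
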